5.1. Efficacy Outcomes

5.1.1. Best Overall Response

Best overall response (BOR) for a patient is the best response designation as assessed by the investigator, recorded between the date of the first dose of study treatment and the date of objectively documented progression per RECIST v1.1 or the date of treatment discontinuation, whichever occurs first. The BOR will be categorized as a complete response/remission (CR), a partial response/remission (PR), a stable disease (SD), or a relapsed/progressive disease (PD). Patients who cannot be evaluated for response will be categorized as Not Evaluable (NE). Patients with an overall response of CR or PR must have a repeat tumor assessment performed no less than 4 weeks (28 days) after the criteria for response are first met. Patients with an overall response of SD must have a minimum duration of 35 days (6 weeks – 1 week window = 35 days). The confirmatory scan is valid following treatment discontinuation as long as the patient has not started a new anti-cancer therapy. BOR will be reported in listings for all patients and summarized for each of the expansion cohorts.

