10.7. End of Treatment Visit

Patients may voluntarily withdraw from the study treatment at any time for any reason, and without prejudice to further treatment. In addition, patients may be withdrawn by the Investigator if they do not feel the patient is deriving clinical benefit or because the patient is experiencing unacceptable toxicity. The reasons for which a patient may be prematurely discontinued are listed in Section 5.10.

Patients who withdraw or are removed from the study treatment will have an end of treatment visit within 7 days of the decision to discontinue study treatment. All study evaluations described below will be performed. Additionally, these patients will undergo a 28-day follow-up safety visit. The eCRF will capture reasons for withdrawal.

The procedures listed below are to be undertaken at the end of treatment visit and documented in the eCRF:

- Symptom-directed physical examination (Appendix A and Appendix B)
- Vital signs as outlined in Section 8.6, Appendix A and Appendix B
- Pulse oximetry (Section 8.8) Weight (Appendix A and Appendix B)
- ECOG performance status (Appendix A and Appendix B)
- Clinical laboratory tests (Section 8.10, Appendix A and Appendix B):
 - Serum chemistry
 - Hematology
- Blood sample for measurement of homocysteine and methylmalonate as outlined in Section 7.2.3 and Appendix C
 - Ophthalmic examinations: visual acuity, fundoscopic exam, ocular symptom assessment (Section 5.8.8)
 - Single, 12-lead ECG (Section 8.7)
 - Radiologic imaging to monitor tumor response if PD has not been documented already (Appendix A and Appendix B)

ImmunoGen, Inc. Confidential Page 103 of 138

 CA125 - for patients with EOC, primary peritoneal cancer, fallopian tube cancer or uterine cancer (Appendix F)

NOTE: patients experiencing CA125 response must have a confirmatory test performed at least 28 days after initial response is documented.

- AEs and SAEs (Appendix A and Appendix B)
- Ocular symptom assessment (Section 5.8.8)
- Concomitant medications (Appendix A)
- HAHA and HADA sample collection as outlined in Section 6 and Appendix C

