10.8. Follow-up Assessments

Safety Follow-up: A safety follow-up visit will occur 28 days (+ 14 days) after the last treatment. During this visit, the following assessments will be performed.

- Complete physical examination (Appendix A and Appendix B)
- Vital signs (Section 8.6, Appendix A and Appendix B)
- Pulse oximetry (Section 8.8)
- Weight (Appendix A and Appendix B)
- ECOG performance status (Appendix A and Appendix B)
- 12-Lead ECG (if clinically indicated)
- Pregnancy test for WCBP (Appendix A and Appendix B)
- Clinical laboratory tests (Section 8.10, Appendix A and Appendix B):
 - Serum chemistry
 - Hematology
 - Coagulation profile
 - Urinalysis
- Radiologic imaging to monitor tumor response if PD has not been documented already (Appendix A and Appendix B)
- For patients with EOC, uterine cancer or NSCLC only:
- CA125 for patients with EOC, primary peritoneal cancer, fallopian tube cancer or uterine cancer (Appendix F)

NOTE: patients experiencing CA125 response must have a confirmatory test performed at least 28 days after initial response is documented.

- AEs and SAEs (Appendix A and Appendix B)
- Ocular symptom assessment (Section 5.8.8)

ImmunoGen, Inc. Confidential Page 104 of 138

- Complete ophthalmic examination for all patients; alternatively, the complete examination can be performed at the End of Study visit.
 - Patients experiencing an ocular treatment-emergent adverse event (Section 5.8.8.2) will continue to have examinations every 2 weeks until the condition resolves or is deemed to be irreversible by the investigator.
- Concomitant medications(Appendix A and Appendix B)
- Directed neurological examination will be performed, to include light touch, pinprick, proprioception, and deep tendon reflexes (DTRs) of the upper and lower extremities; and questioning for symptoms of paresthesia and numbness. If abnormal, an NCI CTAE grade will be recorded and if warranted a neurologist will be consulted (Appendix A and Appendix B)
 - o Neurotoxicity Questionnaire (FACT/GOG NTx), Version 4.0 (Appendix G)
- HAHA and HADA sample collection as outlined in Section 6 and Appendix C

All serious adverse events, and those adverse events assessed by the Investigator as at least possibly related to study drug should continue to be followed until they resolve or stabilize, whichever comes first.

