CR, complete response; PR, partial response; SD, stable disease; PD, progressive disease; UE, unable to evaluate; NA, not applicable (no such lesions at screening); Any, CR, PR, SD, PD, NA or UE. The overall response at a given time point does not depend upon the overall response assigned at any prior time-point.

Best Overall Response

ImmunoGen, Inc. Confidential Page 135 of 138

Protocol 0401

Best overall response is determined once all the data for the patient is known. Best overall response is defined as the best response across all time-points.

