5.1.3. Progression Free Survival (PFS)

PFS is defined as the time from the date of the first dose of study drug until the date of progressive disease or death from any cause, whichever occurs first. PFS is defined based on radiological assessments and determined by the investigator. Clinical progression is not considered a progression endpoint. PFS will be calculated using the following:

- Patients who did not die or have PD will be censored at the date of their last radiological assessment.
- Patients who had PD or death after missing two or more consecutive radiological assessments (PD or death date – last radiological assessment date +1 >=105 days) will be censored at the last adequate radiological assessment.
- Patients who had no baseline or post-baseline radiological assessment(s) will be censored on Day 1 unless the patient died within 105 days of Day 1; in that case, the patient will be considered as having an event at the date of death.
- Patients who started a new anti-cancer therapy prior to documented PD or death will be censored at the last radiological assessment prior to initiation of new anti-cancer therapy.
- When an analysis cutoff date is implemented, only data (deaths and radiological assessments) occurring on or prior to the cutoff date will be used for analysis.

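### SAP 5.1.1 closes the best-overall-response window at an undefined treatment discontinuation date, so a response first seen later cannot count, contrary to protocol Appendix E

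*SAP*

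**What the plan says.** SAP 5.1.1 takes best overall response (BOR) from the first dose to "the date of objectively documented progression per RECIST v1.1 or the date of treatment discontinuation, whichever occurs first". It makes one allowance for scans after treatment stops: "The confirmatory scan is valid following treatment discontinuation as long as the patient has not started a new anti-cancer therapy". SAP 5.1.2 builds ORR on that BOR, over the Response-Evaluable population. SAP 5.1.4 and 5.1.6 define duration of response (DOR) and time to response (TTR) only for responders.

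Protocol Appendix E sets a different rule: "Best overall response is determined once all the data for the patient is known", and "Best overall response is defined as the best response across all time-points". Protocol 11.4, which defines the response rate, has no cut-off at discontinuation.

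The protocol also plans scans after treatment stops:
- Section 10.7: patients who stop "will have an end of treatment visit within 7 days of the decision to discontinue study treatment", and that visit includes "Radiologic imaging to monitor tumor response if PD has not been documented already".
- Section 10.8: "A safety follow-up visit will occur 28 days (+ 14 days) after the last treatment", with imaging on the same condition.
- Section 10.8 and Appendix A footnote j: patients who stop for reasons other than progression are then assessed every 12 weeks (±3 weeks).

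For PFS the SAP uses another cut-off: "Patients who started a new anti-cancer therapy prior to documented PD or death will be censored at the last radiological assessment" before that therapy. SAP 5.1.5 does the same for TTP.

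**The concern.** The protocol collects scans after discontinuation in order to follow response, and the SAP then bars them from showing a first response. SAP 3.7.2 has no matching limit: any post-dose tumor assessment can qualify a patient for the denominator. A patient whose only post-dose scan comes after discontinuation can therefore be counted as evaluable but never as a responder.

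The error runs one way, towards a lower ORR, and it falls on patients who stop early without progression, for example for toxicity. TTR and DOR omit the same patients, and ORR and PFS for one patient can rest on different scans. The SAP states that it is based on Amendment 10 but neither mentions nor justifies the departure from Appendix E.

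**Working it through.** No figure in the plan depends on this rule. The nearest is the chance of at least one response in 40 patients at a true rate of 20%: 1 − 0.8^40 = 0.99987, which agrees with the stated 99.9% and is unaffected.

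**1. Which scans fall outside the window.** The SAP gives no definition of the discontinuation date, so three readings are tried. On Schedule A the dose of cycle c falls on Day 21(c − 1) + 1, and the even-cycle scan on Day 18 ± 3 of that cycle (Appendix A).

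- *Date of last dose.* After a last dose in Cycle 2 (Day 22), the regular scan is on Days 36–42, which is 14–20 days outside. After a last dose in Cycle 1 (Day 1), it is 35–41 days outside. End-of-treatment scans after that dose, 28-day scans and 12-weekly scans are also outside.
- *Date of the decision to stop.* The end-of-treatment scan comes 0–7 days later, so only a same-day scan counts. The 28-day scan is normally outside, and the 12-weekly scans are outside.
- *Date of the end-of-treatment visit or form.* The end-of-treatment scan can be inside. Later scans are normally outside.

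The answer for an end-of-treatment scan therefore depends on an unstated choice. For a first response at a later follow-up scan it generally does not.

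**2. One patient followed through (assumed dates).** Last dose Day 22, immediate stop for toxicity on Day 29, end-of-treatment scan on Day 29 + 7 = Day 36 showing a first partial response. The scan is 36 − 22 = 14 days late by last dose, 36 − 29 = 7 days late by decision date, and inside by visit date. On the first two readings BOR is not evaluable, yet the scan meets the post-dose assessment condition of SAP 3.7.2.

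**3. Confirmation still applies.** SAP 5.1.1 requires a repeat assessment at least 28 days later, here Day 36 + 28 = Day 64 or after. The follow-up visit falls on Day 22 + 28 = Day 50 to Day 22 + 42 = Day 64, so it could confirm only on its last permitted day. Otherwise confirmation waits for the 12-weekly scan and must precede new therapy. Not every such response would be recovered by changing the window.

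**4. Size per affected patient.** The change in ORR is 1/N. Planned N comes from SAP 2.3.3.2 and the groups from SAP 5; the 20% rate is assumed, and intervals are exact 95%.

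| Group | N | 1/N | All counted | One lost |
|---|---|---|---|---|
| Pooled ovarian (cohorts 1, 3, 5: 40 + 20 + 40) | 100 | 1 point | 20/100 = 20.0% (12.7–29.2) | 19/100 = 19.0% (11.8–28.1) |
| 40-patient cohort alone (protocol 11.4) | 40 | 2.5 points | 8/40 = 20.0% (9.1–35.6) | 7/40 = 17.5% (7.3–32.8) |
| Endometrial cohort | 20 | 5 points | 4/20 = 20.0% (5.7–43.7) | 3/20 = 15.0% (3.2–37.9) |

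**5. An illustrative total.** If 10% of patients stopped before any scan showed response and 30% of them responded afterwards, the loss would be 0.10 × 0.30 = 0.03, or 3 points. Both inputs are assumptions. Because of step 3 this is an upper bound on those inputs.

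**The case against.** The best defense is that the rule may be deliberate: response must begin on drug and may be confirmed afterwards, which fits the explicit allowance for the confirmatory scan. PFS and TTP are different endpoints and need not share a window. Nor does a cut-off at new therapy reproduce Appendix E literally, since Appendix E has no cut-off at all. An on-treatment BOR is indeed a legitimate quantity. But the SAP does not say that it intends one, does not define the date, and leaves the denominator without the same limit. The confirmatory-scan allowance supports a response already seen; it does not admit a first one.

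Several narrowing points stand. Scans are due at 6 weeks ± 1 (about Days 36–50), and a patient stopped for failure to recover within 21 days of a Cycle 3 dose due on Day 43 stops after Day 64, so an in-window scan should already exist. Footnote j also waives the end-of-treatment or 28-day scan if one was done in the previous 6 weeks. The cases at issue are mainly early, immediate stops and late first responses.

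A reader might infer more than the documents support:
- *That every response at an end-of-treatment scan is lost.* This depends on the undefined date.
- *That progression is widely under-recorded.* Progression after discontinuation becomes not evaluable only when there is no earlier in-window assessment, and ORR is unchanged because both are non-responses.
- *That the RP2D is in doubt.* ORR is secondary and descriptive, no hypothesis is tested, and Amendment 10 already equates MTD and RP2D on safety data.

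All lesion and RECIST assessments are listed (SAP 5.2.8), so individual cases would remain visible.

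**Conclusion.** The point holds in a limited form. SAP 5.1.1 and Appendix E give different definitions of BOR. Under the SAP's, a response first seen after the discontinuation date cannot count while the patient can remain in the denominator. ORR is biased downward relative to Appendix E, and TTR and DOR lose the patient.

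The patients affected are those who stop without progression, first respond afterwards, and are confirmed at least 28 days later before new therapy. The documents do not give their number, so no total bias can be stated; the 3-point figure should not be read as an estimate. The per-patient effects rest on planned cohort sizes and would be slightly larger if fewer patients are response-evaluable. The one-patient shifts are small against the width of the intervals, but they all go in the same direction. This should be corrected, but it does not threaten the primary objectives.

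**What to change.** In SAP 5.1.1, replace the treatment-discontinuation limit with the start of new anti-cancer therapy. BOR would then use every RECIST assessment from first dose to the earlier of documented progression or new therapy. This agrees with SAP 5.1.3, SAP 5.1.5 and the confirmatory-scan sentence, and comes much closer to Appendix E. State in the SAP that progression and new therapy still end the window, since Appendix E sets neither limit.

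If an on-treatment BOR is also wanted, define the discontinuation date (last dose, decision, or end-of-treatment visit) and report it as a sensitivity analysis.

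The cost is one phrase and the matching program change. The scans are already scheduled, and SAP 1.1 allows changes until database lock.

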5.1.2. Objective Response Rate

The objective response rate (ORR) will be calculated as the number of subjects with a BOR of CR or PR divided by the number of subjects in the Response-Evaluable population. Subjects without at least one post-baseline RECIST assessment will be treated as non-responders. ORR with 95% confidence intervals will be reported for each group.

5.1.3. Progression Free Survival (PFS)

PFS is defined as the time from the date of the first dose of study drug until the date of progressive disease or death from any cause, whichever occurs first. PFS is defined based on radiological assessments and determined by the investigator. Clinical progression is not considered a progression endpoint. PFS will be calculated using the following:

- Patients who did not die or have PD will be censored at the date of their last radiological assessment.
- Patients who had PD or death after missing two or more consecutive radiological assessments (PD or death date – last radiological assessment date +1 >=105 days) will be censored at the last adequate radiological assessment.
- Patients who had no baseline or post-baseline radiological assessment(s) will be censored on Day 1 unless the patient died within 105 days of Day 1; in that case, the patient will be considered as having an event at the date of death.
- Patients who started a new anti-cancer therapy prior to documented PD or death will be censored at the last radiological assessment prior to initiation of new anti-cancer therapy.
- When an analysis cutoff date is implemented, only data (deaths and radiological assessments) occurring on or prior to the cutoff date will be used for analysis.

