8.14. Tumor Response Assessment

Tumor response for patients with measurable lesions should be assessed using RECIST 1.1 (Eisenhauer 2009, Appendix E). Patients with ovarian and uterine cancer will have CA125 measured at approximately the same time they undergo radiologic assessment. Patients will have a baseline tumor assessment done within the 28 days prior to Cycle 1, Day 1. Patients with measurable lesions should be assessed using CT scan approximately every second cycle, from the date of first dose until the 28-day Follow-up visit. Although progression may be determined by the investigator based upon clinical deterioration, every effort should be made to document progression using radiographic methods. The basis for determination of progression per clinical deterioration should be documented.

Patients experiencing CA125 response must have a confirmatory test performed at least 28 days after initial response is documented. In the case of stable disease (SD), follow-up measurements must have met the SD criteria at least once after study entry at a minimum interval of 6 weeks.

Electronic copies of radiologic images with tumor size measurements, including baselines assessment, must be sent to the sponsor within 4 weeks after PR/CR has been documented, together with a copy of the corresponding radiology report and tumor assessment worksheets. Scans must be in Digital Imaging and Communications in Medicine (DICOM) format. Electronic transfer of scan files (via FTP, HTTP, or similar means) is preferred, although transfer on physical media (such as DVD or CD) is acceptable. For digital media, one time point/patient/disk is expected. The site is expected to maintain a copy of digital data for the retention period applicable to the protocol, Good Clinical Practices (GCP), and federal, international, and/or state legal and medical requirements. ImmunoGen will retain the media for

ImmunoGen, Inc. Confidential Page 88 of 138

a period of 2 years following the date a marketing application is approved or, if no application is to be filed or if the application is not approved for such indication, until 2 years after the investigation is discontinued.

Note: It is very important that the same method of radiologic assessment be used throughout the study and that the same lesions are followed.

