Response Follow-up: Patients who have discontinued study treatment for reasons other than PD will be followed per Revised Response Criteria (RECIST 1.1, see Appendix E) every 12 weeks (+/- 3 weeks) until documentation of PD, or until the patient starts subsequent anti-cancer therapy, whichever comes first.

ImmunoGen, Inc. Confidential Page 105 of 138

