11.4. Efficacy

Objective response rate (ORR) - The best OR will be determined by the Investigator for each patient as either CR, PR, SD or relapsed disease/PD. Objective responses for patients in the dose escalation phase will be summarized by dose cohort assigned as well as the dose at which the response occurred. Responses will be tabulated separately for expansion cohorts 1-4. For each expansion cohort, the response rate will be calculated as the number of CR or PR divided by the number of response evaluable patients. To meet the definition of response-evaluable, patients must have undergone radiographic assessment at baseline, received at least one dose of IMGN853, and must have had at least one post-dose tumor assessment.

Duration of Response (DOR) – DOR, defined as the time from initial response until progressive disease, will be estimated for all patients who achieve a confirmed objective response (PR or CR) using the method of Kaplan-Meier. Results will be summarized by dose cohort assigned as well as the dose at which the response occurred.

Progression Free Survival (PFS) – PFS, defined as the time from initiation of study drug until progressive disease or death whichever occurs first, will be estimated using the Kaplan-Meier method. Results will be summarized by dose cohort.

Time to Progression (TTP) - TTP defined as the time from initiation of study drug until progressive disease, will be estimated using the method of Kaplan-Meier. Results will be summarized by dose cohort.

For DOR, PFS, and TTP calculations, subjects not achieving the endpoint will be censored at the time of the last endpoint assessment. Median response times and associated 95% CIs will be presented for descriptive summaries.

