3.7.2. Response-Evaluable Population

To meet the definition of response-evaluable, patients must have
EITHER:

- received a radiographic assessment at baseline,
- received at least one dose of IMGN853, and

- have had at least one post-dose tumor assessment;

OR

- have died within 105 days of receiving their first dose, or
- have clinically progressed within 105 days of receiving their first dose.

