5.1.5. Time to Progression

Time to progression (TTP) is defined as the time from the date of the first dose of study drug until the date of progressive disease. TTP is defined based on radiological assessments and determined by the investigator. Clinical progression is not considered a progression endpoint. TTP will be censored as follows:

- Patients who did not have PD will be censored at the date of their last radiological assessment.

- Patients who had PD after missing two or more consecutive radiological assessments (PD date – last radiological assessment date +1 >=105 days) will be censored at the last adequate radiological assessment.
- Patients who had no baseline or post-baseline radiological assessment(s) will be censored on Day 1.
- Patients who started a new anti-cancer therapy prior to documented PD will be censored at the last radiological assessment prior to initiation of new anti-cancer therapy.
- When an analysis cutoff date is implemented, only radiological assessments occurring on or prior to the cutoff date will be used for analysis.
- Patients who died prior to PD will be censored at the last radiological assessment.

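### SAP PFS and TTP exclude clinical progression without explaining the difference from the protocol, so clinical-only progressors are censored informatively and no sensitivity analysis bounds the upward bias

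*SAP*

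**What the plan says.** **Protocol.** Section 8.14 prefers imaging but accepts a clinical call: "Although progression may be determined by the investigator based upon clinical deterioration, every effort should be made to document progression using radiographic methods". It adds: "The basis for determination of progression per clinical deterioration should be documented". Section 11.4 gives "PFS, defined as the time from initiation of study drug until progressive disease or death whichever occurs first", and TTP in the same terms without death. Neither definition is limited to radiological progression.

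**SAP.** Section 5.1.3 bases PFS on radiological assessments and says "Clinical progression is not considered a progression endpoint". Section 5.1.5 is parallel: "TTP is defined based on radiological assessments and determined by the investigator. Clinical progression is not considered a progression endpoint". The censoring rules that then apply are:
- no PD or death: censored at the last scan;
- new anti-cancer therapy before documented PD or death: censored at the last scan before that therapy;
- no baseline or post-baseline scan: censored on Day 1, except that for PFS a death within 105 days of Day 1 is an event;
- PD or death 105 days or more after the last scan: censored at the last adequate scan;
- TTP only: a death before PD is censored at the last scan.

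**Response analysis.** SAP 3.7.2 makes patients evaluable if they "have clinically progressed within 105 days of receiving their first dose". SAP 5.1.2 counts patients with no post-baseline RECIST assessment as non-responders.

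The SAP says it is based on Amendment 10. The available text gives no reason for the radiology-only restriction and no analysis that counts clinical progression.

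**The concern.** A patient whom the investigator has declared progressed on clinical grounds is a known failure. Under the SAP that patient leaves the risk set at an earlier scan as if still progression-free. Kaplan-Meier assumes that censored patients have the same prospects as those who remain. Here they are removed because they are failing, so the curve is lifted.

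Early clinical progressors show the effect most clearly. ORR counts them as failures, while PFS may let them contribute nothing after Day 1.

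The study tests no hypothesis, so no alpha or power is at stake. PFS and TTP are descriptive secondary endpoints, and their estimates are meant to guide development, including the planned PFS plots by prior regimens and FRα staining in the platinum-resistant EOC patients. A bias of known direction and unknown size should be made visible.

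**Working it through.** The documents give no PFS figure, event count or share of clinical progressions, so there is no planned number to reproduce. The check has two parts.

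**1. Applying the rules to single patients (illustrative dates)**

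*Patient A.* Stable disease on the Day 43 scan, clinical progression on Day 62, new therapy on Day 75. Counting clinical progression gives an event on Day 62. The SAP censors on Day 43. An exit scan need not intervene: Appendix A, footnote j, asks for one only if none was done in the previous 6 weeks, and 62 − 43 = 19 days.

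*Patient B.* Clinical progression on Day 30, no post-baseline scan, alive. SAP 3.7.2 makes the patient response-evaluable and SAP 5.1.2 counts a non-responder. SAP 5.1.3 censors PFS on Day 1.

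A clinical progressor escapes censoring in two ways: a scan shows PD before new therapy and within the window, or, for PFS only, death falls inside the 105-day window without prior new therapy. Either event is dated later than the clinical progression. In TTP, death recovers nothing.

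**2. Size under assumed inputs**

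*Closed form.* With constant hazard λ and a share q of failures censored at about their failure time, the estimated hazard is (1 − q)λ and the median is multiplied by 1/(1 − q):
- q = 5%: 1/0.95 = 1.05
- q = 10%: 1/0.90 = 1.11
- q = 20%: 1/0.80 = 1.25
- q = 30%: 1/0.70 = 1.43

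*Simulation with the SAP rules.* 200,000 patients per scenario, with scans every 42 days (the Schedule A interval). The assumed inputs are exponential time to progression with latent median 120 or 150 days, median survival after progression 60 or 180 days, and new therapy in 0-50%. Deaths inside the window count for PFS and there are no exit scans. The comparator counts clinical progression on its date. Results for 6-month PFS at latent median 150 days:

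| Clinical share | Slow deaths (180 d), 50% new therapy | Fast deaths (60 d), no new therapy |
|---|---|---|
| 5% | 45.9% → 47.5% (+1.6) | 45.6% → 46.5% (+0.9) |
| 10% | 45.7% → 48.9% (+3.2) | 45.3% → 47.1% (+1.8) |
| 20% | 45.4% → 52.1% (+6.7) | 45.3% → 48.9% (+3.6) |
| 30% | 45.1% → 55.6% (+10.5) | 44.8% → 50.4% (+5.6) |

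Over both latent medians the excess is 0.9-1.6 points at 5%, 1.8-3.4 at 10%, 3.6-6.9 at 20% and 5.6-10.9 at 30%.

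*What moves the figure.* At latent median 120 days and a 20% share, the excess is about 8 points if no deaths are counted, about 6 with deaths, and about 3 if half of the clinical progressors also have an exit scan showing PD. Allowing for this spread gives the working ranges: about 1-2 points at 5%, 1.5-4 at 10%, 3-8 at 20% and 4-12 at 30%. The excess is lower still when exit scans and early deaths both recover events.

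*Medians.* These move in steps because of the 42-day grid. At latent median 120 days, median PFS goes from 126 days to 126 at a 5% share and to 153-168 at 20%. Median TTP at 20% goes from 133 to 168 days in the slow-death setting and from 168 to 210 in the fast-death setting.

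**The case against.** **Radiology-only PFS is legitimate.** It is explicit, and more objective in an open-label, uncontrolled study. A reader might infer that the SAP overrides a protocol rule making clinical progression a PFS event. The documents do not support that. Section 8.14 concerns tumor assessment and does not name PFS or TTP. Section 2.4 lists both under RECIST 1.1 and CA-125 response, Appendix E defines PD by lesions only, and Section 11 leaves the full analysis to the SAP. Reading progressive disease in Section 11.4 as RECIST PD is fair. What stands is an unexplained difference in wording.

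**Later scans may exist.** A reader might infer that clinical progressors usually have none, since response follow-up covers those who stopped for other reasons: "Patients who have discontinued study treatment for reasons other than PD will be followed". But Sections 10.7 and 10.8 list imaging at End of Treatment and at 28 days if PD is not already documented, and Appendix A, footnote j, adds a scan if the last is over 6 weeks old. Whether a clinical call counts as documented PD is unclear. How many are rescued cannot be said.

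**Cohort differences.** A reader might infer that the bias is larger in Cohorts 3, 4 and 5, which accept non-measurable disease. This is unsupported: under Appendix E such disease can progress radiologically through non-target or new lesions.

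**Partial transparency.** SAP 4.2 tabulates Clinical Progression as an End of Study reason, SAP 5.2.8 lists censoring, and OS is reported. ORR and PFS may also properly use different rules. This helps, but no planned table shows how many PFS censorings follow clinical progression or what PFS would be if they were events.

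**Conclusion.** The point holds as an unexplained difference between protocol and SAP, with informative censoring of clinical-only progressors and no sensitivity analysis in the available text. The direction is upward for PFS and TTP: simulated 6-month PFS under the SAP rule was above the comparator in every scenario with a clinical share above zero. The size is not established. The ranges above rest on assumed clinical shares, progression and survival times, new-therapy use and exit scanning, none of which the documents give. At a 5% share the effect is 1-2 points and the median does not move; at 20-30% it could matter to a descriptive reading. No single figure for overstatement of PFS can be drawn from the documents. The radiological definition is not wrong in itself. This is an inexpensive improvement to a descriptive analysis.

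**What to change.** Before database lock, until which the SAP can still be modified:

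1. Keep the radiological-only PFS and TTP in SAP 5.1.3 and 5.1.5, and state why they are narrower than the wording of Protocol 8.14 and 11.4.
2. Add a sensitivity analysis of PFS and TTP for each analysis group, in which investigator-documented clinical progression is an event on its date and all other censoring rules are unchanged.
3. Beside each radiological result, report the number of patients censored after clinical progression.

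The patients can be identified from the End of Study category Clinical Progression and from the End of Treatment reasons. A progression date is implied by the 105-day rule in SAP 3.7.2, but its presence on the eCRF should be confirmed.

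The cost is SAP wording and one more set of Kaplan-Meier tables. The downsides are a less objective event type in the added analysis and a somewhat less favourable PFS beside the main one.
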